6.4.2 Secondary Analysis

Secondary endpoints are expressed as change from Week 0 to Week 12. Those that are measured at baseline (Week 0), Week 6 and Week 12 will be analyzed as the primary endpoint, with the exception that tests will be conducted at the 0.05 significance level. Those measured at baseline (Week 0) and Week 12 only will be analyzed with an analysis of covariance (ANCOVA) model including treatment group and baseline value. Because it is expected that the distribution of hsCRP will be skewed, a log-transformation will be applied to hsCRP data prior to analysis. Geometric mean and geometric mean percent change will be added to the descriptive statistics that will be presented.

6.4.3 Exploratory Analysis

Similarly, exploratory endpoints are expressed as change from Week 0 to Week 12. Those that are measured at baseline (Week 0), Week 6 and Week 12 will be analyzed as the primary endpoint, with the exception that tests will be conducted at the 0.05 significance level. Those measured at baseline (Week 0) and Week 12 only will be analyzed with an ANCOVA model including treatment group and baseline value. Because it is expected that the distribution of triglycerides will be skewed, a log-transformation will be applied to triglycerides data prior to analysis. Geometric mean and geometric mean percent change will be added to the descriptive statistics that will be presented.

6.4.4 Sensitivity Analysis

6.4.4.1 Per-Protocol Analysis

The analysis of the primary endpoint described in section 6.4.1 will be repeated on the PP population. The tests will be conducted at the 0.05 significance level.

To better understand the impact of compliance, the same analysis will be repeated on a modified version of the PP population where the compliance criteria will be set to 70%. In other word, the analysis of the primary endpoint will be conducted in patients who had a compliance of at least 70% and no major protocol deviations that could affect the primary endpoint.

6.4.4.2 Dose-Response Analysis

In order to visualize the dose-response relationship, a regression model including linear and quadratic terms will be used to characterize the relationship between dose level (considered as a continuous variable) and the change from Week 0 to Week 12 in direct-measured LDL-C. More specifically, the model will be:

$$Y_j = \beta_0 + \beta_1 d_j + \beta_2 d_j^2 + \varepsilon_j$$

where Y_j is the change from Week 0 to Week 12 of the j^{th} patient, β_0 is the intercept, β_1 is the coefficient of the linear dose term, β_2 is the coefficient of the quadratic dose term, d_j is the dose level (0g, 1.5g, 3g, 6g) and ε_j is the error term. A test of the null hypothesis $H_0: \beta_2 = 0$ versus the alternative hypothesis $H_1: \beta_2 \neq 0$ will be performed at the 0.05 significance level. Non rejection of the null hypothesis will result in dropping the quadratic term from the model and concluding that a linear relationship provides a better fit. Otherwise, the quadratic term will be kept in the model. A plot of the predicted dose-response curve with 95% CIs will be provided to visualize the dose response relationship, along with the estimate of the coefficients β_1 and β_2 (if applicable) with associated 95% CI and p-values.

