6 STATISTICAL METHODOLOGY

6.1 Determination of Sample Size

Sample size computation was based on the change in LDL-cholesterol. Based on previous literature, we are expecting a mean decrease from baseline to follow-up in LDL-C of -0.30 mmol/L (11.6 mg/dl) in the placebo group and we are aiming to show that the addition of beta-glucan, either at 1.5 g, 3 g or 6 g, will further reduce LDL-C by -0.30 mmol/L, leading to an expected difference in change in LDL-C of 0.30

mmol/L between the placebo group and at least one of the active groups. The expected standard deviation of the change in LDL-C is 0.50 mmol/L (19.3 mg/dl). To reach a power of 80% in detecting this 0.30 mmol/L difference with a two-tailed significance level of 0.0167 (to account for three main comparisons (placebo vs. beta-glucan 1.5 g, placebo vs. beta-glucan 3 g and placebo vs. beta-glucan 6 g), 60 subjects per group were needed for a total of 240 subjects. To account for approximately 9% lost to follow-up, 264 subjects (66 subjects per treatment group) were randomized.

Sample size was calculated with nQuery + nTerim 2.0.

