6.2 Statistical Considerations

This is a randomized, parallel study with four treatment groups (placebo, beta-glucan 1.5 g, beta-glucan 3 g and beta-glucan 6 g). The statistical analysis will focus on the comparisons of the three active groups vs. placebo.

Descriptive statistics of all study variables will be presented overall and broken down by treatment group. Number of observations, mean, standard deviation, median, minimum and maximum will be presented for continuous variables. Count and proportion will be displayed for categorical variables.

Basic assumptions of the proposed analyses will be checked and data transformation or other analyses could be done if appropriate. For example, as some endpoints are likely to be skewed (ex. triglycerides, hsCRP), log-transformation might be used, in which case descriptive statistics would also include geometric means.

Laboratory parameters will be assigned to visits based on number of days from randomization and not based on scheduled visit at which the measurement was made. The time windows that will be used to assign measurements to visits are given in Appendix 2.

Values entered as less than a specified value will be considered as the specified value divided by 2 (e.g. entered value <0.2 will be analyzed as 0.1). Values entered as BLQ (Below Limit of Quantification) will be considered as the limit of quantification divided by 2. Values entered as more than a specified value will be considered as the specified value.

All statistical tests will be two-sided. Tests involving the comparisons of the active groups vs. placebo for the primary endpoint will be conducted at the 0.0167 significance level. All other tests will be considered secondary or exploratory and will be conducted at the 0.05 significance level.

No interim analysis on efficacy endpoints is planned for this study.

Statistical analyses will be done using SAS version 9.4 or higher.

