6.4.1 Primary Analysis

The primary endpoint is the change from Week 0 to Week 12 in direct-measured LDL-C. The changes, as well as the LDL-C values at each study visit, will be summarized with descriptive statistics.

The primary endpoint will be compared between treatment groups using a repeated measures analysis of covariance (ANCOVA) model.. More specifically, the dependent variable will be the change from Week 0 in LDL-C (change calculated as post Week 0 level – Week 0 level) the model will include treatment group, time (Week 6 and Week 12) and treatment group x time interaction as well as the covariates of Week 0 value of LDL-C and Week 0 value of LDL-C x time interaction. An unstructured covariance structure will be

used to model the within-patient errors and the Kenward-Roger approximation will be used to estimate denominator degrees of freedom. Contrasts under this model will allow for the three main comparisons: placebo vs. beta-glucan 1.5 g, placebo vs. beta-glucan 3 g and placebo vs. beta-glucan 6 g. More specifically, the following hypotheses will be tested:

$$H_0: \Delta_{W12,\text{placebo}} = \Delta_{W12,1.5g} \quad \text{vs.} \quad H_1: \Delta_{W12,\text{placebo}} \neq \Delta_{W12,1.5g}$$

$$H_0: \Delta_{W12,\text{placebo}} = \Delta_{W12,3g} \quad \text{vs.} \quad H_1: \Delta_{W12,\text{placebo}} \neq \Delta_{W12,3g}$$

$$H_0: \Delta_{W12,\text{placebo}} = \Delta_{W12,6g} \quad \text{vs.} \quad H_1: \Delta_{W12,\text{placebo}} \neq \Delta_{W12,6g}$$

where $\Delta_{W12,\text{placebo}}$, $\Delta_{W12,1.5g}$, $\Delta_{W12,3g}$ and $\Delta_{W12,6g}$ are respectively the mean change from Week 0 to Week 12 in LDL-C in the placebo, beta-glucan 1.5 g, beta-glucan 3 g and beta-glucan 6 g group.

All sets of hypotheses will be tested at the 0.0167 significance level to maintain the overall type I error to 0.05 for the primary endpoint. These tests will be considered as the primary analysis of the study.

For illustrative purposes, changes within groups will be tested at the 0.05 significance level. Estimates of the changes within groups and of the between-group differences will also be presented along with 95% confidence intervals.

The same ANCOVA model will also allow for the examination of the change from Week 0 to Week 6 in LDL-C. In other words, the hypotheses described above will also be tested at Week 6 at the 0.05 significance level for illustrative purposes.

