| 3.6 Laboratory parameters | |
| Table 3.6.1 | Summary of hematology laboratory results, safety population |
| Table 3.6.2 | Summary of biochemistry laboratory results, safety population |

| | |
|----------------|--|
| Figures | |
| Figure 1 | Subject disposition (flow chart) |
| Figure 2 | Plot of predicted change from Week 0 to Week 12 in direct-measured LDL-C (mg/dL) with 95% CIs against dose level, ITT population |

| | |
|-----------------|------------------------|
| Listings | |
| Listing 1 | Subject disposition |
| Listing 2 | Datasets analyzed |
| Listing 3 | Protocol deviations |
| Listing 4 | Demographics |
| Listing 5 | Adverse events |
| Listing 6 | Serious adverse events |
| Listing 7 | Laboratory results |
| Listing 8 | Deaths |

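### The dose-response rule in SAP 6.4.4.2 takes a non-significant quadratic term as evidence for a straight line, and its model is the only efficacy model without the baseline value

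*SAP*

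**What the plan says.** SAP 6.4.4.2, under Sensitivity Analysis, writes the dose-response model in full: an intercept, a linear dose term, a quadratic dose term and an error, with doses 0, 1.5, 3 and 6 g. The quadratic coefficient is tested at 0.05. Non-rejection "will result in dropping the quadratic term from the model and concluding that a linear relationship provides a better fit". The output follows from whichever model is kept: "A plot of the predicted dose-response curve with 95% CIs will be provided to visualize the dose response relationship". The coefficients are reported too, but the quadratic one only "if applicable) with associated 95% CI and p-values".

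The output list in SAP section 7 has one efficacy figure, Figure 2: "Plot of predicted change from Week 0 to Week 12 in direct-measured LDL-C (mg/dL) with 95% CIs against dose level, ITT population". It lists no dose-response table. The protocol contains no dose-response analysis, so this SAP text is the only specification.

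The other efficacy models adjust for baseline. The primary model (6.4.1) includes treatment, time and their interaction "as well as the covariates of Week 0 value of LDL-C and Week 0 value of LDL-C x time interaction", and the per-protocol analyses repeat it. Secondary endpoints follow the primary model or, if measured only at Week 0 and Week 12, are "analyzed with an analysis of covariance (ANCOVA) model including treatment group and baseline value". Sections 6.4.3 (exploratory) and 6.4.5 (subgroups) also include the baseline value.

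**The concern.** There are two separate points.

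First, the drop rule prescribes a conclusion that the test cannot deliver. Failing to reject a zero quadratic coefficient shows only that curvature was not detected. A line nested in a quadratic can never have the smaller residual sum of squares, so in the literal sense it cannot fit better. The trial was sized for dose-versus-placebo contrasts of 0.30 mmol/L, not for curvature. Once the term is dropped, the line is drawn with ordinary confidence limits, and the reader may never see how imprecise the curvature test was. If the effect levels off, the figure can show the highest dose ahead of the middle one when they are equal.

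Second, the missing Week 0 term puts Figure 2 on a different footing from Table 2.1.1, although both describe the same Week 12 change in LDL-C. Some precision is also given up. This does not cause the first problem, and correcting it does not cure that problem.

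**Working it through.** **Inputs from the SAP.** Doses are 0, 1.5, 3 and 6 g. There are 60 evaluable subjects per group; pooled placebo is 3 × 22 = 66 randomized, the same as each active group. "The expected standard deviation of the change in LDL-C is 0.50 mmol/L". Tests are two-sided, at 0.05 for the quadratic term. **Assumed:** the true dose-response shapes, because the documents give none.

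**The plan's own figure first.** For a difference of 0.30, SD 0.50 and two-sided alpha 0.0167, the noncentral t gives 79.5% power at 59 per group and 80.3% at 60. Then 240 / 0.91 = 263.7, or 264. The stated sample size reproduces. The plan states no power for the quadratic test.

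**Precision of the quadratic coefficient.** SE = SD / √(n × R), where R is the residual sum of squares of dose² after regression on dose over the four levels.
- Mean dose is 2.625, and the sum of squares of dose is 19.6875.
- The cross-product with dose² is 122.344, and the sum of squares of dose² is 823.922.
- R = 823.922 − 122.344² / 19.6875 = 63.64.
- SE = 0.50 / √(60 × 63.64) = 0.00809.

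**Plateau from 3 g (0, -0.15, -0.30, -0.30 mmol/L against placebo).**
- The least-squares quadratic coefficient is 0.01515, so the noncentrality is 0.01515 / 0.00809 = 1.87. With 237 df, power is 46% and the term is dropped in 54% of trials.
- Slope of the retained line = −0.95625 / 19.6875 = −0.0486 per g. Intercept = −0.1875 + 0.0486 × 2.625 = −0.06.
- Relative to that fitted placebo value, 3 g is 3 × −0.0486 = −0.146 and 6 g is 6 × −0.0486 = −0.291. The gap is 0.146 mmol/L (× 38.67 = 5.6 mg/dL), against a true gap of 0.

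**The whole two-stage rule, by simulation** (at least 40,000 trials per shape, n = 60, SD 0.50):

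| True change vs placebo at 0, 1.5, 3, 6 g | Term dropped | Dropped and significant downward line | Line vs fitted placebo: 3 g, 6 g | True 6 g minus 3 g |
|---|---|---|---|---|
| 0, -0.15, -0.30, -0.30 | 54% | 49% | -0.15, -0.29 | 0 |
| 0, -0.20, -0.30, -0.30 | 44% | 38% | -0.14, -0.27 | 0 |
| 0, -0.30, -0.30, -0.30 | 26% | 20% | -0.12, -0.24 | 0 |
| 0, -0.20, -0.20, -0.20 | 59% | 26% | -0.08, -0.16 | 0 |
| 0, 0, -0.30, -0.30 | 80% | 78% | -0.17, -0.34 | 0 |
| 0, -0.075, -0.15, -0.30 (linear) | 95% | 88% | -0.15, -0.30 | -0.15 |
| 0, 0, 0, 0 | 95% | 2.4% | 0, 0 | 0 |

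In the first row, the plotted 95% interval at 3 g covers the true arm mean in 18% of trials that drop the term, and in 55% of all trials. Under the linear and null shapes, the final model covers 93% at 3 g and about 95% at 6 g.

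**Sensitivity of the first row.** For SD 0.40 to 0.60 the term is dropped in 36% to 66% of trials. With all 66 per group it is dropped in 50%. About 135 per group would be needed for 80% power to detect this curvature.

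**Keeping the quadratic regardless.** In the first row the expected difference between 6 g and 3 g becomes −0.02. For the 0.30 plateau from 1.5 g, however, the quadratic puts 6 g about 0.06 worse than 3 g, and its 3 g interval covers 85%. It is not a cure.

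**Baseline term.** The SE ratio is √(1 − ρ²), where ρ is the correlation of Week 0 LDL-C with the change (assumed). For ρ = 0.3 it is 0.954, and for ρ = 0.5 it is 0.866, so standard errors fall by about 5% to 13%. Power for the quadratic in the first row rises only from 46% to 50% or 58%.

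**The case against.** The strongest reply is that little depends on this analysis. It is a visualization under Sensitivity Analysis, with no rule that selects a dose. The primary analysis gives baseline-adjusted, shape-free estimates for every arm with 95% intervals, reported in Table 2.1.1. A reader who consults that table will not be misled about 3 g and 6 g. All of this stands, and it sets the weight.

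The harm also depends on a shape that the documents do not specify, and under a linear or null truth it is negligible. That stands too.

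It can be said that the SAP meant only that the simpler model is adequate. The text says more than that, and rewording removes the doubt. SAP 6.2 also says: "Basic assumptions of the proposed analyses will be checked and data transformation or other analyses could be done if appropriate". That is a general permission and does not alter the explicit rule in 6.4.4.2.

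On the baseline term, the outcome is already a change score and the gain in precision is modest. That is fair; what remains is the inconsistency and a covariate that costs nothing.

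Three stronger readings are tempting but not supported:
- **That the line exaggerates 6 g against placebo.** With true placebo set to 0, the fitted level at 6 g is -0.35 against a true -0.30, but the same line puts placebo at -0.06. Against its own placebo value, 6 g is -0.29, about right. The error in that case is an understated 3 g effect. Across the five plateau shapes, only the one with no effect at 1.5 g overstates 6 g, by 0.04.
- **That the dose conclusion would rest on Figure 2.** Table 2.1.1 already carries the comparisons.
- **That leaving out Week 0 LDL-C biases the curve.** Doses are filled in successive tiers (SAP 2.1), so a drift in baseline between tiers is possible, but the documents give neither its size nor its direction. Without such a drift, the omission costs precision only.

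**Conclusion.** The concern holds at low weight, as an optional improvement. The instruction to conclude that the line fits better is wrong as written. Under an assumed plateau from 3 g, with the SAP's 60 per group and SD of 0.50, about half of trials (49%) would drop the quadratic and present a significant downward line. That line halves the 3 g effect and shows 6 g about 0.15 mmol/L ahead when the true gap is 0. Other assumed plateaus give 20% to 78%; a linear or null truth gives little harm.

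The missing baseline value is a separate inconsistency with every other efficacy model. It is worth about 5% to 13% in standard error if the assumed correlation is 0.3 to 0.5. Adding it would also guard against any Week 0 imbalance between the successive tiers.

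The three primary comparisons and their error control are untouched.

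**What to change.** In SAP 6.4.4.2 and Figure 2:

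- (a) Replace the better-fit conclusion with a statement that no departure from linearity was detected.
- (b) Report the quadratic coefficient from the quadratic model with its 95% interval, whatever its p-value.
- (c) Overlay on Figure 2 the baseline-adjusted Week 12 arm means with 95% intervals already planned in 6.4.1, in the mg/dL units of Table 2.1.1.
- (d) Add Week 0 LDL-C to the dose-response model and plot predictions at its overall mean.

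Items (a) to (c) do not change how often the term is dropped. They stop the line from being read alone as the shape of the dose response. Item (d) puts the curve on the same baseline-adjusted footing as Table 2.1.1.

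The cost is a short edit to one SAP section, a covariate already collected, and an overlay of estimates already planned. The only downside is a slightly busier figure.

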6.4.5 Subgroup Analysis

The following subgroup analyses are planned for the primary endpoint:

- Hypercholesterolemia according to median of direct-measured LDL-C at baseline,
- Hypercholesterolemia according to quartiles of direct-measured LDL-C at baseline,
- Male vs female,
- Diabetic vs non-diabetic,
- Hypertensive vs non-hypertensive,
- Age < 65 years old vs. age ≥ 65 years old,
- Age according to quartiles,
- Treated with a statin at baseline vs. not treated with a statin at baseline (based on variable DS_STATIN on the Randomization Form of the electronic case report form (eCRF)).

For subgroup analyses, ANCOVA models on the change from Week 0 to Week 12 in LDL-C will be used. These models will include a factor for the Week 0 value of LDL-C, as well as factors for the treatment

group, the subgroup variable and the treatment group x subgroup variable interaction. This interaction term will determine the impact of the subgroup on the treatment effect. For illustrative purposes, estimates of treatment effect will be presented within each subgroup. The tests will be conducted at the 0.05 level for the ITT population.

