6.2.1 Handling of Missing Data

For efficacy laboratory endpoints, the screening value will be taken if the baseline value is missing.

In addition, the proposed statistical analysis will account for all available data and will not disregard subjects with missing data at either Week 6 or Week 12. However, in subjects who will only have a baseline measurement, the last observation carried forward approach will be used.

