Because the SAS procedure PROC MIXED will be used, subjects with missing data at a given study visit will not be excluded from the analysis.

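### The subgroup analyses use a Week 12-only ANCOVA with no rule for a missing Week 12 value, so subjects whose last LDL-C is at Week 6 drop out, although the primary model keeps them

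*SAP*

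**What the plan says.** **Subgroup model (SAP 6.4.5).** "ANCOVA models on the change from Week 0 to Week 12 in LDL-C will be used". The terms are listed: "These models will include a factor for the Week 0 value of LDL-C, as well as factors for the treatment" groups, the subgroup variable and their interaction. Neither time nor Week 6 appears. On level and population: "The tests will be conducted at the 0.05 level for the ITT population". Protocol 10.3.4 has the same model.

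**Primary model (SAP 6.4.1).** Here "the model will include treatment group, time (Week 6 and Week 12) and treatment group x time interaction", together with baseline LDL-C and its interaction with time, an unstructured covariance and Kenward-Roger degrees of freedom. The section draws the consequence itself: "Because the SAS procedure PROC MIXED will be used, subjects with missing data at a given study visit will not be excluded from the analysis".

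**Missing data (SAP 6.2.1).** The planned analysis "will account for all available data and will not disregard subjects with missing data at either Week 6 or Week 12". The next sentence adds that "in subjects who will only have a baseline measurement, the last observation carried forward approach will be used". For a change score, that means a change of zero.

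**Visit assignment (SAP 6.2 and Appendix 2).** Laboratory values are assigned by day since randomization: days 3 to 63 count as Week 6, and day 64 onward as Week 12.

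**The concern.** A model whose only outcome is the Week 12 change cannot use a subject who has Week 0 and Week 6 values but no Week 12 value. The label is ITT, which SAP 3.1 defines as all randomized patients, yet these subjects contribute nothing to the subgroup models.

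The windows add to the group. Protocol 6.11 encourages subjects who leave early to complete the Visit 4 procedures. If that sample is taken before day 64, it is filed under Week 6, and the subject still has no Week 12 outcome.

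Two things are at stake. Tables 2.4.1 to 2.4.8 would rest on a different model, and possibly a different set of subjects, from Table 2.1.1, with no reason given. The subgroup estimates would also be closer to completer estimates, which are more exposed to selective dropout than a model that conditions on the Week 6 response.

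**Working it through.** **1. Is the single-time-point reading right?** SAP 6.4.1 calls the primary model repeated measures. SAP 6.4.2 and 6.4.3 use plain ANCOVA for endpoints measured only at Week 0 and Week 12. SAP 6.4.5 uses the plain term, names the Week 12 change as the outcome and lists its terms without time. The reading is well supported, although 6.4.5 never states the exclusion.

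**2. The plan's own figures (SAP 6.1).** Inputs: two-sided alpha 0.0167, power 80%, difference 0.30 mmol/L, SD 0.50 mmol/L.
- Normal approximation: n = 2(z₁₋α/₂ + z₁₋β)² SD²/δ², which rounds up to 59 per group.
- Noncentral t: power is 79.5% at 59 and 80.3% at 60, so 60 per group, as stated.
- Loss of 9%: 60/0.91 = 65.9, so 66 per group. 240/0.91 = 263.7, so 264 in total.
- Planned losses: 264 − 240 = 24 (9.1%), or 6 per group.

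**3. Who enters the subgroup model?** Let k of the 6 losses per group have Week 6 data only (assumed; the documents give no split). The other 6 − k have baseline only and, if the carry-forward rule applies, stay in with zero change. The model then uses 66 − k per group.

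| k per group | Subjects in subgroup model | Subjects in primary model |
|---|---|---|
| 0 | 264 | 264 |
| 3 | 252 | 264 |
| 6 | 240 | 264 |

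If the carry-forward rule does not reach the subgroup models, baseline-only subjects are lost too, and the count is 240 for any k.

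**4. Precision.** Let m be the fraction with Week 6 but no Week 12 value, and ρ the correlation between the two changes. Relative to one unit of variance per subject, the Week 12 arm mean has variance
- Week 12 only: 1/(1 − m)
- using Week 6: (1 − ρ²)/(1 − m) + ρ²

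The ratio is (1 − ρ²) + ρ²(1 − m) = 1 − mρ², so the reduction is mρ².

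| | ρ = 0.5 | ρ = 0.8 |
|---|---|---|
| m = 0.03 | 0.03 × 0.25 = 0.8% | 0.03 × 0.64 = 1.9% |
| m = 0.09 | 0.09 × 0.25 = 2.3% | 0.09 × 0.64 = 5.8% |

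With 60 completers and 6 Week-6-only subjects in an arm, the effective n is 60/(1 − ρ² × 6/66): 61.4 at ρ = 0.5 and 63.7 at ρ = 0.8.

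**5. Bias, as an illustration only.** Simulation with 66 per arm, mean changes −0.30 (placebo) and −0.60 (active) at both visits, and SD 0.50. The assumed dropout after Week 6 was 9% at random on placebo. On active, its log-odds rose by 1 per SD of poorer Week 6 response. About 11% were missing overall. The true difference is −0.30.

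| ρ | Week 12 only | Using Week 6 |
|---|---|---|
| 0.5 | −0.329 | −0.301 |
| 0.7 | −0.339 | −0.301 |

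This is a whole-arm comparison. It carries over to within-subgroup effects. The interaction test is biased only if the selection differs between subgroup levels.

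**The case against.** **The model is deliberate and acceptable.** Protocol and SAP prespecify the same Week 12 ANCOVA, which is a standard model for an interaction test. Differing from the primary model is not in itself an error. This stands. The weakness is the lack of any provision for a missing Week 12 value when a model that uses those subjects is already specified.

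**A reader might infer that 6.4.5 flatly breaches 6.2.1, with an inverted inclusion rule that keeps baseline-only subjects and discards better-observed ones.** The documents do not support that so firmly. The promise in 6.2.1 speaks of one proposed analysis and echoes the PROC MIXED sentence in 6.4.1, so it may describe the primary model alone. The inversion requires the carry-forward half of 6.2.1 to operate in the subgroups while the other half fails, which is possible but not stated. On the other side, 6.2.1 sits under general considerations and opens with a rule for all efficacy laboratory endpoints. On the narrow reading, nothing covers a missing Week 12 value in the subgroups. The carried-forward zero also feeds the primary model, so it does not distinguish the two analyses.

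**The number may be small.** Protocol 4.3 and 5.5 keep subjects who stop the product in follow-up, and any sample from day 64 counts as Week 12. This stands: 24 is a ceiling.

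**A reader might also infer that bias is likely because dropout rises with tablet load, or that the trial's title poses a statin comparison.** Neither is documented. The documents give no dropout figure by dose. The title describes the population, and no objective compares statin users with non-users.

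**Conclusion.** The concern holds at a modest size. As written, the subgroup models have no outcome for subjects whose last LDL-C is in the Week 6 window, while the primary model uses them and 6.2.1, read generally, promises to. At most about 24 of 264 subjects are affected at the planned loss rate. The forgone precision is 0.8% to 5.8% of the variance of an arm mean, which rests on the assumed m and ρ. Bias is possible if dropout after Week 6 depends on the Week 6 response, but the documents neither show nor rule that out. SAP 6.2 classes all non-primary tests as secondary or exploratory, and 6.4.5 calls the within-subgroup estimates illustrative, so no primary conclusion is touched. It is an inexpensive improvement, not a flaw that threatens the trial.

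**What to change.** In SAP 6.4.5, fit the subgroup analyses in the primary repeated-measures model, keeping the unstructured covariance and Kenward-Roger. Add subgroup, subgroup × time, treatment × subgroup and treatment × subgroup × time. Take the interaction test and the within-subgroup contrasts at Week 12, so that subgroup and primary tables use the same subjects. Align the dose-response regression in 6.4.4.2, which is also Week 12-only.

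If the sponsor prefers the single-time-point model, 6.4.5 should at least state one consistent rule for a missing Week 12 value, covering both Week-6-only and baseline-only subjects.

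**Cost.** SAP wording and programming; no new data. The models grow: a quartile subgroup gives 4 × 4 × 2 = 32 cell means, with about 16 subjects per treatment-by-quartile cell (264/16 = 16.5 on average). Those cells are as sparse under the present model, but the added time terms make the fit more demanding.

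**What it leaves open.** The zero change carried forward for baseline-only subjects remains. It also affects the primary analysis and is a separate issue.
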